6.2 Screening Assessments

Screening assessments will be performed prior to CEUS imaging. Trial participants will have the presence of inclusion criteria and absence of exclusion criteria verified by providing a medical history. A full demographic profile, known drug allergies or intolerances, and a review of the subject's medical/surgical history will be recorded. If the subject is a woman of childbearing age, she will have a urine pregnancy test (the results of which will be made available to the subject prior to study initiation) prior to each ultrasound exam. A brief abdominal ultrasound (without contrast) will also be performed prior to radioembolization to ensure the target lesion is visible on ultrasound.

6.3 Ultrasound Imaging

All contrast injections will be supervised by a board certified physician. Resuscitation equipment and trained personnel will be in immediate proximity to the patient during each CEUS exam. The ultrasound examinations will be performed by a qualified sonographer. Ultrasound exams will take place 1-6 hours post radioembolization in Thomas Jefferson University's short procedure recovery unit, and approximately 7, and 14 days post treatment in Thomas Jefferson University's Ultrasound Division.

Procedures and equipment for this trial will be used in accordance with typical clinical procedures. All trial procedures will be conducted in accordance with Good Clinical Practice. For the ultrasound examination, the patient will be asked to lie in a supine or decubitous position and a catheter will be placed in a superficial vein (preferably an antecubital vein). Acoustic coupling gel will be applied to the area of interest. A state of the art, commercially available ultrasound scanner with curvilinear probe will be used. All acoustic parameters will be well within FDA limits. Imaging will be performed by an ultrasonographer with experience in liver imaging using an S3000 or Sequoia scanner with a 6C1, 5C1 or DAX probe and flashreplenishment and a nonlinear imaging package (Siemens Medical Solutions, Mountain View, CA). Ultrasound exams will take place 1-6 hours post radioembolization in Thomas Jefferson University's short procedure recovery unit, and 7, and 14 days post treatment in Thomas Jefferson University's Interventional Radiology or Ultrasound Division. Both of these locations have full time nursing support and with patient physiological monitoring. All contrast injections will be supervised by a board certified physician with resuscitation equipment in immediate proximity during contrast-enhanced ultrasound (CEUS) exam. The entire ultrasound imaging protocol will require approximately 90 mins including a 30 min observation period. These time points are based on times when patients are still present or returning to the hospital for regular follow up and when the Y-90 spheres are still active. Patient vital signs will be monitored and recorded throughout the visit.

CEUS studies will only be conducted with patients assigned to the experimental group (UTMD + radioembolization). Five milliliters of activated Optison will be suspended in 50 ml of saline and infused through an angiocatheter placed in a peripheral arm vein at a rate of 120 ml/hour. This total Optison administration falls within the product insert dosage guidelines (up to 5 ml within a 10 minute period and up to 8.7 ml in any one study). After confirmation of contrast-enhancement within the mass, a series of ultrasound-triggered microbubble destruction (UTMD)-replenishment sequences will be generated to cavitate UCA within the imaging plane. The patient will be asked to temporarily halt respiration while a 4 second UTMD pulse is initiated (approximate transmit parameters of MI = 1.13 at 1.5 MHz, transmitting 2.3 µs pulses at a pulse repetition frequency of 100 Hz), followed by nonlinear imaging of contrast replenishment at lower intensity using Cadence Pulse Sequencing (MI = 0.06) for 10 seconds. Following patient respiration, this sequence will be repeated at multiple imaging planes throughout the tumor and then repeated throughout the entire tumor volume for the duration of the infusion (UTMD expected in 10-20 planes, repeated 3-4 times). In the few patients with multiple Y-90 treated tumors, the largest tumor will be selected for UTMD therapy and outcomes compared to the non-UTMD treated tumors outside the acoustic field. This sequence will be repeated at imaging planes throughout the tumor for the duration of the infusion. Following completion of the infusion, patients receiving ultrasound contrast agent will be monitored for adverse events for 30 minutes to ensure stable response.

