The primary measure of tumor response will be evaluated using mRECIST criteria as determined by Drs. [name] and [name] in consensus using the patients clinically scheduled 3-4 month contrast enhanced MRI or CT. As a secondary measure of tumor response, changes in alpha fetal protein (AFP; collected as blood samples at approximately one month post embolization as standard of care) will be recorded when clinically available. Tumoral perfusion for each imaging plane will also be calculated as the slope of contrast reperfusion based on change in signal intensity over time. Perfusion values for each plane will then be averaged over the entire mass and normalized to values immediately post treatment (day 1). Finally, each patient's progression free survival and overall survival will be monitored, although this is a tertiary outcome for this study and many patients are expected to surpass the timeline of this pilot study. Safety outcomes will be determined using changes in vital signs, observed and self-reported adverse events, and changes in liver function tests (LFTs) at approximately 1 month post-embolization when available (preformed as part of clinical standard of care). Liver function tests (LFTs) include blood tests for alanine aminotransferase, alkaline phosphatase, asparate aminotransferase, bilirubin, albumin, total protein, and prothrombin time. SPECT imaging will be evaluated for all available cases by two blinded radiologists to evaluate if the initial UTMD session skews Therasphere distribution in the liver.

The proposed agent for the current study, Optison™ is a sterile non-pyrogenic suspension of encapsulated perflutren microbubbles [Goldberg et al 2001; Miller & Nanda 2004]. The contrast agent is consists of a human serum albumin shell with perflutren core and contains 5.0 - 8.0 x 10⁸ microspheres/ ml. The microbubble agent is supplied in a standard-size 3 ml vial and is prepared by manually shaking the vial. Optison will be stored in a secure refrigerator, with only the study investigators and research personnel having access. Optison is currently only approved for use in echocardiography. The agent will be used as an off-label indication for this study, but within approved dosage recommendations.

Statistical Methodology: This project is a pilot study to determine if microbubble destruction and reperfusion can used to improve treatment response of HCC to radioembolization and predict early treatment response.

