To answer the secondary hypothesis of whether contrast reperfusion can predict treatment outcomes earlier than conventional MRI/CT imaging at 3-4 months, changes in imaging data from the experimental group will be quantified. The contrast replenishment time intensity curve will be fit with a 2-parameter exponential recovery curve: $VI = \alpha(1 - e^{-\beta t})$, in which VI represents video intensity; α (decibels) represents the asymptotic plateau correlative of the microvessel cross-sectional area, and β (in mm/s) represents the blood velocity. The product $\alpha \times \beta$ is an estimate of perfusion or blood flow per tissue unit (approximately ml/(s mg)) [Krix et al. 2003]. Parametric images from multiple slices in the tumor will also be compiled into a parametric volume to enable visualize of perfusion throughout the mass. Regions of interest will then be selected by Drs. [name] and [name] to determine average perfusion of the mass, peripheral perfusion, and vascular heterogeneity. These values will be quantified for each time point and normalized to D-CEUS at day 1. Normalized values will be grouped based on tumoral response as complete response, partial response, stable disease, and progressive disease (based on mRECIST by 3-4 month contrast-enhanced MRI/CT) to determine if D-CEUS provides an earlier indication of treatment response. Finally, changes in perfusion during the same infusion will be quantified to determine if tumor vascularity is altered during the process of UTMD.

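### Aim 2 perfusion is normalized to the first exam, but nothing keeps a patient on one ultrasound system, and the curve is fitted to decibels with β in mm/s

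*Combined protocol and SAP*

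**What the plan says.** **Equipment.** Section 6.3 of the Combined protocol and SAP, and the synopsis under Trial Procedures, allow an "S3000 or Sequoia scanner with a 6C1, 5C1 or DAX probe". Section 6.3 adds that "Procedures and equipment for this trial will be used in accordance with typical clinical procedures".

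**Location.** The first exam is in the recovery unit. The later ones are elsewhere: section 6.3 has "short procedure recovery unit, and 7, and 14 days post treatment" in the "Interventional Radiology or Ultrasound Division". The synopsis names only the first of those two divisions, and an earlier paragraph of section 6.3 names only the second.

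**Endpoint.** Section 6.5 fits VI = α(1 − e^(−βt)), takes α × β as perfusion, and states: "These values will be quantified for each time point and normalized to D-CEUS at day 1". The synopsis also normalizes to the first exam. On units, section 6.5 says: "α (decibels) represents the asymptotic plateau correlative of the microvessel cross-sectional area, and β (in mm/s) represents the blood velocity".

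**Analysis.** Section 7.2 correlates the normalized values with mRECIST by Spearman's method in the experimental arm. Section 7.2.1 claims at least 80% power for a correlation of 0.4 with 52 patients, and plans a confounding check for this aim that does not name equipment.

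We found no rule that holds scanner, probe, gain, dynamic range or depth constant within a patient, and none for cross-calibration, conversion to linear intensity or recording the system used at each exam.

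**The concern.** There are two separate faults.

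**Equipment.** α is a plateau of displayed signal, so it depends on the system and its receive settings as well as on the tumor. Normalizing to the first exam removes that dependence only if system and settings are the same at both exams, and the plan does not secure this. If some patients change system and others do not, the change alters the ordering of patients, and a rank correlation does not protect against that.

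**Scale.** The exponential describes refilling in quantities proportional to bubble concentration. Decibels are logarithmic, so the fitted α and β no longer carry the meanings that section 6.5 gives them, and a ratio of their product is not a ratio of blood flow. The stated unit of β is also impossible in the stated formula.

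At stake are the strength of the Aim 2 correlation and the truth of any perfusion change reported as a number.

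**Working it through.** **1. The plan's own figure.** Inputs from section 7.2.1: n = 52, correlation 0.4, two-sided 5%. Power = Φ(atanh(ρ) × √((n − 3)/v) − 1.96), with atanh(0.4) = 0.4236.
- v = 1.06 (Fieller): 0.4236 × √(49/1.06) = 2.88, power 82%.
- v = 1 (Fisher): 84%.
- v = 1 + 0.4²/2 = 1.08 (Bonett-Wright): 81%.

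The claim of at least 80% reproduces, with little margin. Steps 2 and 4 use v = 1.06.

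**2. Effect of a system change.** The documents give no between-system variance, so every input here is an assumption: variance of the log true flow ratio V = 0.74 (SD 0.86), a fraction f of patients switching, and a sensitivity difference d on the log scale of linear intensity (3 dB: ln 2 = 0.693; 6 dB: ln 4 = 1.386). Switching is taken as unrelated to response. Observed correlation = 0.4 × √(V / (V + f(1 − f)d²)).

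| f | difference | f(1 − f)d² | observed correlation | power, n = 52 |
|---|---|---|---|---|
| 0 | none | 0 | 0.400 | 82% |
| 0.1 | 3 dB | 0.043 | 0.389 | 80% |
| 0.1 | 6 dB | 0.173 | 0.360 | 73% |
| 0.3 | 3 dB | 0.101 | 0.375 | 76% |
| 0.3 | 6 dB | 0.404 | 0.322 | 62% |

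This treats intensity as linear. If decibels are fitted as written, a 3 dB sensitivity change with perfusion unchanged (assumed plateau 20 dB, β = 0.3/s) moves the α × β ratio from 1.00 to 1.43, and 6 dB moves it to 2.00. Putting d = ln 1.43 = 0.358 into the formula with f = 0.3 gives f(1 − f)d² = 0.027, correlation 0.393 and power 81%. V on the decibel scale is unknown too.

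**3. Decibel scale and units.**
- The exponent βt must be a pure number. With t in seconds, β is per second; mm/s × s leaves millimetres.
- An offset common to both exams does not cancel in a decibel ratio: 30/20 = 1.50, but with 6 dB added to both, 36/26 = 1.38.
- Assumed curves I(t) = 1 + A(1 − e^(−bt)) over 10 seconds were converted to decibels and refitted with the two-parameter form. With true b = 0.3/s, fitted β runs from 0.73 at A = 10 to 2.1 at A = 300. It therefore depends on the plateau as well as on velocity.
- A true doubling of b from 0.2 to 0.4 reads as 1.78 at a 10 dB plateau and 1.65 at 30 dB. Read backwards, a halving shows as 1/1.78 = 0.56 to 1/1.65 = 0.61. Over all the curves tried, a true halving of flow read between 0.52 and 0.81.
- In simulated pairs of exams, the rank correlation between the decibel ratio and the true ratio was about 0.98.

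**4. Cost of excluding switched patients.** At 30% switching, 52 × 0.7 leaves 36 patients. Power = Φ(0.4236 × √(33/1.06) − 1.96) = Φ(0.40) = 66%. That is below the 76% for keeping them at a 3 dB difference and only slightly above the 62% at 6 dB.

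**The case against.** **Switching is inferred from silence.** A reader might infer that the protocol expressly permits a patient to change system. It does not: the list of equipment can equally be read as covering a recruitment period of 83 months, and a change of room need not be a change of scanner. This stands. What remains is that nothing prevents a switch.

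**The power loss is not established.** A reader might take the figures in step 2 as the trial's actual loss. Every input is assumed, and at 10% switching with 3 dB, or with the decibel-scale shift, power stays at about 80% to 81%. This stands too.

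**Processing may remove part of the effect.** The formula has no offset term, which suggests that a post-flash baseline is subtracted, although the plan does not say. In a refit (A = 100, b = 0.3/s), a pure gain of 3 or 6 dB on signal and noise floor alike left α × β at 28.45 after subtraction; without subtraction it rose to about 42 and 60. A difference in sensitivity relative to the noise floor would still matter.

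**Not every perfusion measure is exposed.** Section 6.5 also plans a comparison within one infusion, which a change of system between exams cannot affect. It would be wrong to say that all of the CEUS analysis is compromised.

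**Ranks and the confounding check.** The Spearman test is nearly immune to the decibel scale, so that fault is one of reported size and meaning. The check in section 7.2.1 could include equipment, but only if the system is recorded.

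**Conclusion.** The point holds as a measurement weakness in the secondary aim. The normalized perfusion value is protected against equipment effects only if each patient stays on one system and settings, and the plan does not require that. The expected harm is a weaker correlation: power of about 80% to 62% against 82%, wholly under the assumed 10% to 30% switching and 3 to 6 dB differences. The documents do not support a claim that switching occurs, or how often. A reader might also infer a risk of false-positive findings, but equipment noise unrelated to response attenuates a correlation and does not create one.

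The scale fault needs no assumption about conduct. β in mm/s is inconsistent with the formula, and α × β from decibel data is not proportional to flow. The distortion of reported changes (a halving read as about 0.5 to 0.8) depends on assumed curves. Its effect on the planned rank test is small.

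These results read "normalized" as a ratio. If a difference in decibels is meant, an offset that differs between exams still enters. The primary mRECIST comparison does not use perfusion and is unaffected.

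**What to change.** **Section 6.3:** state that all CEUS exams of one patient use the same scanner model, probe and saved preset as the first exam wherever possible, and that the system used is recorded at each exam. Keep exams done on another system in the analysis, flag them, and add a sensitivity analysis restricted to patients with unchanged equipment. Mandatory exclusion is not advised, for the reason in step 4 of the working.

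**Section 6.5:** fit the curve to linearised intensity and give β in s⁻¹.

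Both changes are needed. Linearising alone leaves a 3 dB system change as a factor of 2 in α; fixed equipment alone leaves a ratio that is not a flow ratio.

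The cost is a short addition to each section, a saved preset per patient, an occasional scheduling constraint when a scanner is in use, and one linearisation step in processing.

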Protocol Title: Ultrasound Microbubble Destruction for Improving Radioembolization Therapy of Hepatocellular Carcinoma

Trial Objectives: The primary objective of this trial is to:

· Characterize the ability of localized ultrasound contrast agent destruction to improve hepatocellular carcinoma (HCC) response to Y90 radioembolization.

The secondary aim of this trial is to:

· determine if contrast-enhanced ultrasound estimated tumor perfusion can reliably predict HCC response to radioembolization 1-14 days post treatment.

Trial Design: This is an open-label, randomized trial that will be conducted at one clinical site to determine if ultrasound-triggered microbubble destruction (UTMD) can be used to improve radioembolization of HCC. The subject population will be patients scheduled for radioembolization of a previously untreated HCC mass at Thomas Jefferson University. Patients will be randomly assigned to either the experimental (UTMD + radioembolization) or control group (radioembolization alone) by the research coordinator using a random assignment generator. For patients assigned to the experimental group, the study will consist of up to three contrast-enhanced ultrasound (CEUS) exams 1-6 hours post radioembolization, and approximately 7 and 14 days post treatment. Treatment response will be evaluated using modified response evaluation criteria in solid tumors (mRECIST) at 1 and 3-4 months post treatment based on the patient's clinically scheduled contrast-enhanced MRI or CT. For patients assigned to the control group, only outcomes data will be collected (without intervention).

Ultrasound imaging will be performed using a state of the art commercial ultrasound scanner with a curvilinear transducer. As part of each CEUS exam, patients will first undergo baseline grayscale B-mode and power Doppler imaging (PDI) of the treated mass. Patients will then receive an infusion of the ultrasound contrast agent (UCA) Optison (GE Healthcare, Princeton, NJ), while being imaged with two-dimensional (2D) dual mode B-mode / coded harmonic imaging. Once the presence of contrast has been confirmed in the tumor, a series of flash-replenishment sequences will be generated to destroy UCA within a region of interest encompassing the tumor. This sequence will be repeated at imaging planes throughout the tumor for the duration of the infusion.

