CEUS studies will only be conducted with patients assigned to the experimental group (UTMD + radioembolization). Five milliliters of activated Optison will be suspended in 50 ml of saline and infused through an angiocatheter placed in a peripheral arm vein at a rate of 120 ml/hour. This total Optison administration falls within the product insert dosage guidelines (up to 5 ml within a 10 minute period and up to 8.7 ml in any one study). After confirmation of contrast-enhancement within the mass, a series of ultrasound-triggered microbubble destruction (UTMD)-replenishment sequences will be generated to cavitate UCA within the imaging plane. The patient will be asked to temporarily halt respiration while a 4 second UTMD pulse is initiated (approximate transmit parameters of MI = 1.13 at 1.5 MHz, transmitting 2.3 µs pulses at a pulse repetition frequency of 100 Hz), followed by nonlinear imaging of contrast replenishment at lower intensity using Cadence Pulse Sequencing (MI = 0.06) for 10 seconds. Following patient respiration, this sequence will be repeated at multiple imaging planes throughout the tumor and then repeated throughout the entire tumor volume for the duration of the infusion (UTMD expected in 10-20 planes, repeated 3-4 times). In the few patients with multiple Y-90 treated tumors, the largest tumor will be selected for UTMD therapy and outcomes compared to the non-UTMD treated tumors outside the acoustic field.

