4.1 Inclusion Criteria

All subjects accepted for this trial must:

- Be scheduled for sub-lobar radioembolization therapy of a previously untreated HCC mass < 6 cm visible on grayscale ultrasound.
- Be at least 18 years of age.
- Be medically stable.
- If a female of child-bearing age, have a negative pregnancy test prior to each ultrasound exam.
- Have signed Informed Consent to participate in the study.

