6. TRIAL PROCEDURES

6.1 Patient Enrollment

Subjects eligible for trial enrollment will be identified by Drs. [name], [name], [name], and [name] from their patient population (approximately 52 patients annually being treated by yttrium-90 for hepatocellular carcinoma). These patients will be accrued from the Hepatology department, as well as from the HCC Multidisciplinary Tumor Board of the Kimmel Cancer Center at Thomas Jefferson University. A research coordinator will explain the study to the patient. The patient will be given time to consider the risks and benefits of the study and ask questions about participation. The coordinator will review the consent form with the patient and then the patient will be given the form to review. The patient, coordinator, and a study investigator will all sign the consent form. The patient will be given a copy of the signed consent form for their records. A research coordinator will explain the study to the patient. The patient will be given time to consider the risks and benefits of the study and ask questions about participation before providing informed consent. If the subject is a woman of childbearing potential, she will have a urine pregnancy test (the results of which will be made available to her prior to study initiation) prior to each ultrasound exam. Patients will be randomly assigned to either the experimental (UTMD + radioembolization) or control group (radioembolization alone) by the research coordinator using a random assignment generator. For patients in the experimental group, a brief abdominal ultrasound (without contrast) will also be performed prior to radioembolization to ensure the target lesion is visible on ultrasound.

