6.5 Efficacy Assessments

The primary measure of tumor response will be evaluated using mRECIST criteria as determined by Drs. [name] and [name] in consensus using the patients clinically scheduled 3-4 month contrast enhanced MRI or CT. As a secondary measure of tumor response, changes in alpha fetal protein (AFP; collected as blood samples at 1 month as standard of care) will be recorded. Finally, each patient's progression free survival and overall survival will be monitored, although this is a tertiary outcome for this study and many patients are expected to surpass the timeline of this pilot study. Safety outcomes will be determined using changes in vital signs, observed and self-reported adverse events, and changes in liver function tests (LFTs) at 1 and month post-embolization (preformed as part of clinical standard of care). Liver function tests

(LFTs) include blood tests for alanine aminotransferase, alkaline phosphatase, asparate aminotransferase, bilirubin, albumin, total protein, and prothrombin time. SPECT imaging will be evaluated for all available cases by two blinded radiologists to evaluate if the initial UTMD session skews Therasphere distribution in the liver.

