7.2 Statistical Analyses

Qualitative findings regarding treatment response will be generated by two radiologists based on mRECIST criteria at 1 and 3-4 months post treatment (using the patient's clinically scheduled contrast-enhanced MRI or CT exams). In the event of conflicting outcome reports, outcomes will be evaluated in consensus.

All statistical analysis will be performed by [name] (SKCC Biostatistics Core and faculty member) using SAS version 9.4 (Cary, NC). Aim 1: The primary hypothesis that UTMD improves the effect of

radioembolization on tumor response in HCC patients will be tested with a non-parametric Mann-Whitney U-test of the difference in response distributions between control (radioembolization alone) and experimental group (UTMD + radioembolization), measured at 3-4 months post treatment. The outcome variable in this analysis, the mRECIST score, is treated as an ordinal variable in this analysis. **Aim 2:** To test if tumor perfusion measured by CEUS between UTMD pulses predicts HCC response to radioembolization, perfusion will be characterized in terms of contrast replenishment time intensity curves fit with a 2-parameter exponential recovery curve as described above. The relationship between the normalized profusion values from this image processing and the patients' subsequent mRECIST scores in the UTMD + radioembolization group will be evaluated with Spearman's rank order correlation.

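### In experimental-arm patients with several treated tumours, UTMD always goes to the largest, so the planned within-patient comparison cannot separate UTMD from tumour size

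*Combined protocol and SAP*

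**What the plan says.** Section 6.3 and the Trial Procedures part of the synopsis carry the same rule for the experimental arm. "In the few patients with multiple Y-90 treated tumors", one tumour is chosen and the others serve as its comparators: "the largest tumor will be selected for UTMD therapy and outcomes compared to the non-UTMD treated tumors outside the acoustic field". No count or percentage of such patients is given.

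Eligibility (Section 4.1) is worded around one mass, "Be scheduled for sub-lobar radioembolization therapy of a previously untreated HCC mass < 6 cm visible on grayscale ultrasound", but does not require a solitary lesion. Controls have no study intervention and supply only outcome data (Section 3).

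On the endpoint, Section 6.5 says "The primary measure of tumor response will be evaluated using mRECIST criteria", read in consensus at 3-4 months. Section 7.2 adds "The outcome variable in this analysis, the mRECIST score, is treated as an ordinal variable in this analysis" and tests it between arms with a Mann-Whitney U-test. Neither section says whether the score belongs to a lesion or to the patient, or which lesion counts when there are several. Section 7.2 gives no analysis for the within-patient comparison. Section 7.2.1 promises to look for confounders and put them in OLS or quantile regression models, but names neither tumour size nor paired lesions.

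**The concern.** A within-patient comparison is attractive because each patient is his or her own control. That holds only if the choice of treated lesion is unrelated to outcome. Here the choice is made on size, and the comparator is never larger than the treated tumour. Randomisation does not help, because it assigns patients and not lesions. Restricting comparators to tumours outside the acoustic field guards against spill-over but leaves the size imbalance in place.

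If size affects response in either direction, that effect is read as an effect of UTMD. A real benefit could be hidden, or an absent one suggested. The protocol also leaves open which lesion supplies the primary score in a patient with several. Response reads are not described as blinded (Section 5.4 rules out blinding, and only the SPECT reads are called blinded), so a lesion rule fixed in advance is worth having.

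**Working it through.** **Stated figure.** The point disputes no number in the plan. The 52 per group reproduces: 2 × ((1.960 + 1.036)/0.6)² = 49.9, and dividing by the Mann-Whitney relative efficiency 3/π gives 52.2.

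**From the documents.** The largest treated tumour gets UTMD, comparators are the patient's other tumours, and the qualifying mass is under 6 cm.

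**Assumed (not in the documents).** Two tumours per patient; sizes uniform on 1-6 cm; logit P(complete response) = 0.5 + slope × (size − 3), with slope 0, −0.2 or −0.4 per cm.

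**Step 1: size gap.** The larger of two uniform draws averages 1 + 5 × 2/3 = 4.33 cm and the smaller 1 + 5 × 1/3 = 2.67 cm, a gap of 1.67 cm.

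**Step 2: hand check at the mean sizes, slope −0.2, no UTMD effect.** Largest: 0.5 − 0.2 × 1.33 = 0.233, giving 55.8%. Other: 0.5 + 0.2 × 0.33 = 0.567, giving 63.8%. The difference is −8.0 points.

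**Step 3: averaged over the size distribution by simulation.** The last two columns add a true UTMD odds ratio of 2 on the largest tumour in the experimental arm.

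| Slope per cm | Largest, no UTMD effect | Other | Difference, no UTMD effect | Difference, odds ratio 2 | Odds-ratio-2 difference minus control-arm difference |
|---|---|---|---|---|---|
| 0 | 62.2% | 62.2% | 0 | +14.5 | 14.5 |
| −0.2 | 55.7% | 63.6% | −7.9 | +7.8 | 15.7 |
| −0.4 | 49.1% | 64.7% | −15.6 | +0.4 | 16.0 |

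The within-patient contrast is biased by the fourth column. At a slope of −0.4 it all but erases a true odds ratio of 2. Subtracting the same contrast in controls returns 0 under the null and 14.5 to 16.0 points when the odds ratio is 2. A patient random effect with SD 1 on the logit scale shrinks the null differences to 0, −6.7 and −13.2. A positive slope would reverse the sign.

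**Step 4: primary test.** Under the null, with 52 per arm, a slope of −0.3 per cm (odds ratio 0.74) and the experimental arm scored on its largest lesion, Mann-Whitney rejection was:

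| Control lesion scored | 10% multi-tumour | 30% multi-tumour |
|---|---|---|
| Largest (same rule) | 5.0% | 4.8% |
| Chosen at random | 5.4% | 4.9% |
| Worst-responding | 5.1% | 7.9% |

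Each cell has 4,000 runs, so the simulation error is about √(0.05 × 0.95/4000) = 0.3 points.

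**Step 5: precision of the remedy.** If 10% of 52 (about 5) patients per arm have several tumours, then at slope −0.2 and ignoring within-patient correlation the standard error is √(2 × (0.557 × 0.443 + 0.636 × 0.364)/5) = 0.44. The 95% half-width is about 1.96 × 0.44 = 0.86, or 86 points.

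**The case against.** The strongest reply is that this is a minor side comparison. It is one clause in procedural text, confined to few patients, and absent from the objectives, the analysis section and the sample-size section. The trial's conclusion rests on the randomised comparison. All of that stands, and it limits the weight of the point. It does not rescue the comparison, which the protocol still states as planned.

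A second reply is that Section 7.2.1 already provides for confounders. That helps little. Within a patient, UTMD and being the largest lesion never separate, so adjusting for diameter would have to borrow the size-response relation from other patients, and no such model is specified.

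A third is that the magnitude is assumed throughout and uses binary complete response, while the endpoint is ordinal. This is correct. The percentages illustrate scale only; the confounding itself does not depend on them.

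A reader might go further and infer that the primary endpoint is scored on different lesions in the two arms, or that controls have no lesion rule at all. The documents do not support either. They are silent on the scoring unit for patients with several tumours, but nowhere say that the arms are handled differently. The same named criteria and consensus read apply to both. Section 6.2 also describes the check that the target lesion is visible without naming an arm, although Section 6.1 ties it to the experimental group.

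**Conclusion.** The point holds for the within-patient comparison. As designed, it cannot be attributed to UTMD, because treatment and being the largest lesion are fully confounded. The bias in complete response is 0 to about −16 percentage points for assumed slopes of 0 to −0.4 per cm, with two tumours of 1-6 cm. It would be tempting to say that the design is biased against UTMD, but the documents give no size-response relation, so even the direction is unknown.

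For the primary test the expected effect is small. Rejection stayed near 5% in every scenario except the pairing of 30% multi-tumour patients with worst-lesion scoring of controls (7.9%), and 30% sits poorly with the protocol's description of such patients as few. What remains there is an unstated scoring unit that is worth settling in advance. It is not a demonstrated bias.

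**What to change.** In Sections 6.5 and 7.2, before outcomes are analysed:

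- Identify the largest Y-90-treated tumour from baseline imaging in every patient, in both arms, and name it the index lesion.
- Score the primary mRECIST category on that lesion in both arms, so that the primary test reflects the tumour UTMD reaches.
- Replace the uncontrolled within-patient comparison with the largest-minus-other contrast compared between the randomised arms. Use a defined scale such as the proportion with complete response, since ordinal categories should not be subtracted. Label it exploratory.
- Define the comparator tumour by a baseline rule that can be applied in both arms, because controls have no acoustic field by which to select it.

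The lesion designation is for measurement only and changes no treatment. The cost is protocol and SAP wording plus lesion-level reading of scans already collected; the 52 per group is unaffected. The downside is precision: with about five multi-tumour patients per arm the interval would span most of the possible range, so the contrast can only be descriptive.
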